#### 8.3.3.7 REPORTING PREGNANCY AS A SERIOUS ADVERSE EVENT

Any pregnancy that occurs during a clinical study that is using an investigational drug must be reported to the DCC utilizing the SAE report form. This report is *for tracking purposes only*. All pregnancies that are identified during the study must be followed to conclusion and the outcome of each must be reported. The investigator will inform the subject if there are any study medications they must stop taking in addition to the belatacept. The investigator should report all pregnancies within 24 hours (as described in section 8.3.3.2) using the SAE report form. The investigator should counsel the subject and discuss the risks of continuing with the pregnancy and the possible effects on the fetus. A woman who becomes pregnant or wishes to while on the study will be counseled as to her choices and will be encouraged to discuss those choices with her obstetrician. Monitoring of the subject should continue until the conclusion of the pregnancy, and a follow-up SAE report form detailing the outcome of the pregnancy should be submitted.

#### 8.3.4 Updating Source Documentation

Documents describing the safety profile of a drug, such as the investigator's brochure, will be amended as needed by the study drug manufacturer to ensure that the description of safety information adequately reflects any new clinical findings. Until these documents are updated, expedited reporting will be required for additional occurrences of a reaction.

## **9. MECHANISTIC ASSAYS**

### **9.1 Metabolic Testing**

#### **9.1.1 Study Endpoints**

Because the assessment of islet graft function is dependent on complex physiologic relationships between the graft and its recipient, no single test adequately addresses the viability of the transplant. Therefore, insulin-independence will be used as a clinically relevant measure of islet graft function for the primary endpoint, and additional stimulatory tests of islet graft function utilizing meal (MMTT) and glucose (FSIGT) challenges will be performed to assess secondary endpoints. Also, the effect of islet graft function on glycemic control (HbA1c), glycemic lability (MAGE and LI), hypoglycemia (Clarke and HYPO scores), glucose variability (CGMS), and QOL) will be assessed as additional secondary endpoints (see Section 4.1.2 for endpoint description).

#### **9.1.2 Metabolic Assessments**

All subjects will use a study provided One Touch® Ultra glucometer or an approved glucometer or CGMS unit identified in the MOP for measuring capillary glucose levels until one year after their final islet transplant. The timing of these metabolic assessments is provided in Appendices 1 - 3.

Subjects may use any glucometer for the metabolic assessments in Appendix 4, during the second year after final islet transplant..

##### **9.1.2.1 INSULIN REQUIREMENTS**

Subjects will record their total daily insulin dose on self-monitoring diaries. Subject should be given exogenous insulin as needed to maintain fasting capillary glucose levels  $\leq 140$  mg/dL (7.8 mmol/L) at a minimum of 4 out of 7 days a week; 2-hour post-prandial capillary glucose levels should not exceed 180 mg/dL (10.0 mmol/L) more than 3 times per week.

##### **9.1.2.2 GLYCEMIC CONTROL**

Glycemic control will be assessed by HbA1c (%), which will be analyzed centrally at the University of Washington.

##### **9.1.2.3 GLYCEMIC LABILITY**

Glycemic lability will be assessed by both the MAGE and the LI measured every 3 months following transplant, including 365 days post-initial transplant.

The MAGE requires 14 - 16 capillary BG measurements over two consecutive days taken before and 2 hours after breakfast, lunch, and dinner, and at bedtime with an optional measurement at 3 AM. A glycemic excursion is calculated as the absolute difference in peak and subsequent

nadir (or vice versa) glucose values, with the direction (peak to nadir versus nadir to peak) determined by the first quantifiable excursion in the two day period. All excursions > 1 S.D. of the 7 – 8 glucose readings for the day in which they occurred qualify for the analysis, where they are summed and divided by the number of qualified excursions to give the MAGE in mmol/L (or mg/dL) glucose. A MAGE > 11.1 mmol/L (200 mg/dL) is indicative of marked glycemic lability.

The LI requires 4 or more daily capillary BG measurements over a 4 week period and is calculated as the sum of all the squared differences in consecutive glucose readings divided by the hours apart the readings were determined (range 1 to 12 hours) in mmol/L/h wk. A LI greater than or equal to the 90th percentile (433 mmol/L/h wk) of values derived from an unselected group of T1D patients is evidence for severe glycemic lability.

#### 9.1.2.4 HYPOGLYCEMIA

An episode of severe hypoglycemia is defined as an event with one of the following symptoms: memory loss; confusion; uncontrollable behavior; irrational behavior; unusual difficulty in awakening; suspected seizure; seizure; loss of consciousness; or visual symptoms, in which the subject was unable to treat him/herself and which was associated with either a blood glucose level < 54 mg/dL (3.0 mmol/L) or prompt recovery after oral carbohydrate, IV glucose, or glucagon administration.

In addition, composite indices of hypoglycemia frequency, severity, and symptom recognition will be assessed by both the Clarke survey and the HYPO score.

The Clarke survey involves subject completion of eight questions scored by the investigator according to an answer key that gives a total score between 0 and 7 (most severe), where scores of 4 or more indicate reduced awareness of hypoglycemia and increased risk for severe hypoglycemic events.

The HYPO score involves subject recording of BG readings and hypoglycemic events (BG < 3.0 mmol/L [54 mg/dL]) over a 4-week period and recall of all severe hypoglycemic episodes in the previous 12- months. A HYPO score greater than or equal to the 90th percentile (1047) of values derived from an unselected group of T1D patients indicates severe problems with hypoglycemia.

#### 9.1.2.5 MIXED-MEAL TOLERANCE TEST (MMTT)

Basal (fasting) and stimulated glucose and c-peptide levels will be determined using the MMTT. Subjects will be instructed not to eat or inject short-acting (or bolus) insulin after 8 PM the night before the test. Evening or bedtime administration of long-acting insulin will be permitted, as will consumption of water. Subjects receiving CSII (insulin “pump” therapy) may remain on the basal rate of insulin. Subjects will arrive fasting to the transplant or diabetes clinic where the capillary BG will be checked. If the BG is < 70 mg/dL (3.89 mmol/L) or > 180 mg/dL (10 mmol/L), the test will be rescheduled for the next possible day. If the BG is 70 – 180 mg/dL (3.89 – 10 mmol/L), basal glucose and c-peptide levels will be drawn. Immediately after, the subject will receive 6 mL per kg body weight (to a maximum of 360 mL) of Boost® High Protein

Drink (or a nutritionally equivalent substitute) to consume in 5 minutes starting at time = 0. Then, at time = 90 minutes, stimulated glucose and c-peptide levels will again be drawn.

Each blood sample collected for c-peptide and glucose determination will be drawn according to University of Washington (Seattle, WA) SOP and will be shipped frozen to U of W for measurement in the core laboratory.

#### 9.1.2.6 B-SCORE: A COMPOSITE INDEX OF POST-TRANSPLANT GRAFT FUNCTION

The  $\beta$ -score will be determined from the HbA1c, insulin requirements, fasting (basal) glucose, and stimulated c-peptide as developed by Ryan et al. The score may range from 0 (no graft function) to 8, with all subjects reported with a score of 8 also having 90-minute glucose levels during a MMTT that are  $\leq 10.0$  mmol/L (180 mg/dL), indicative of excellent graft function.

#### 9.1.2.7 THE C-PEPTIDE (GLUCOSE X CREATININE) RATIO

The c-peptide: (glucose X creatinine) ratio (CPGCR) will be determined from the fasting (basal) glucose and c-peptide, and a simultaneous serum creatinine. This measure accounts for both the dependence of c-peptide secretion on the ambient glucose concentration and the dependence of c-peptide clearance on kidney function. The CPGCR is calculated as [c-peptide (ng/mL) \* 100]/[glucose (mg/dL) \* creatinine (mg/dL)]. An index of islet graft function, this measure correlates well with both the 90-minute serum glucose levels during a MMTT and with the  $\beta$ -score.

#### 9.1.2.8 INSULIN-MODIFIED FREQUENTLY-SAMPLED INTRAVENOUS GLUCOSE TOLERANCE (FSIGT) TEST

The  $AIR_{glu}$ , insulin sensitivity, and disposition index (DI) will be determined using the FSIGT test. This assessment provides a composite measure of  $\beta$ -cell function, the disposition index (DI), which relates the effect of insulin sensitivity on first-phase insulin secretion ( $AIR_{glu}$ ). Understanding the effect of insulin sensitivity on insulin secretory dynamics post-transplant is important because insulin resistance imposes an increased demand on  $\beta$ -cell function to maintain the same level of glycemia. Whether insulin resistance, possibly attributable to immunosuppressive drugs, is an important problem post-transplant is not known. Preliminary data indicate that insulin sensitivity may actually be improved post-transplant, despite immunosuppression, possibly due to the improved glycemia that occurs with transplantation. These results require confirmation by longitudinal analysis.

The insulin-modified FSIGT test involves blood sampling at baseline (t = -10, -5, and -1 min) and at t = 1, 2, 3, 4, 5, 7, 10, 12, 14, 16, 18, 20, 22, 25, 30, 40, 50, 70, 100, 140, & 180 minutes post-injection of glucose at t = -30 seconds with an injection of insulin at t = 20 min. Each pre-transplant blood sample will be used for insulin and glucose determination. Each post-transplant blood sample will be used for insulin and glucose determination; in addition, the

baseline ( $t = -10, -5, \text{ and } -1 \text{ min}$ ) and  $t = 1, 2, 3, 4, 5, 7, \text{ and } 10 \text{ minutes}$  post-glucose injection samples will be used for c-peptide determination.

All samples will be drawn according to University of Washington (Seattle, WA) SOP and will be shipped frozen to U of W for measurement in the core laboratory. The  $\text{AIR}_{\text{glu}}$  is calculated as the incremental area-under-the-curve for insulin between 0 and 10 minutes post-injection (the same calculation can be performed for c-peptide). Glucose effectiveness (SG), a measure of insulin-independent glucose disposal, and insulin sensitivity, a measure of insulin-dependent glucose disposal, are derived from Bergman's minimal model using MinMod Millennium® software, and further allow for determination of the disposition index ( $\text{DI} = \text{AIR}_{\text{glu}} \cdot \text{SI}$ ).

#### 9.1.2.9 CONTINUOUS GLUCOSE MONITORING SYSTEM® (CGMS)

Glucose variability and hypoglycemia duration will be determined using CGMS® (Medtronic Minimed, Northridge, CA). CGMS® involves the SC placement of a glucose sensor connected by tubing to a pager-sized monitoring device that stores glucose data over a 72-hour period. Subjects will have the sensor placed in the diabetes clinic and wear it continuously for 72 – 84 hours. Then they will drop the monitoring device off or ship it to the clinic 4 days later for analysis. Subjects will need to calibrate the sensor to their capillary BG readings 4 times daily with no interval between readings exceeding 12 hours. Data from each 72-hour period will be analyzed for mean glucose concentration, mean glucose variability (absolute value of measured glucose minus 5.5 mmol/L [100 mg/dL]), number and duration of hyper- ( $> 10.0 \text{ mmol/L}$  [180 mg/dL]) and hypo- ( $< 3.0 \text{ mmol/L}$  [54 mg/dL]) glycemic episodes, and total duration of hypoglycemia.

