The HbA1c is the standard measure of glucose control and is used in all major studies as an endpoint of glycemic control. It has been valuable as a risk predictor of diabetes complications. Yet the HbA1c may be misleading. Patients with erratic glucose control, especially if having hypoglycemic unawareness, can have an HbA1c below 7%, yet the most chaotic and difficult glycemic control. Mean glucose values suffer the same problem in that swings in glucose values between 2 and 20 and back to 2 mmol/L may give a mean glucose of 8 mmol/L, a poor reflection of the real state of affairs.

Previous efforts at measuring glucose lability have ranged from qualitative to quantitative. Earlier definitions of brittle diabetes have incorporated visits to the hospital  but these are subject to the vagaries of local practice. More quantitative measures have been the mean amplitude of glycemic excursions (MAGE)  and the M value of Schlichtkrull . The MAGE relies on capillary glucose readings over two days (a minimum of seven readings a day) and an amplitude is an excursion of glucose in excess of the standard deviation of the mean values for the day. If the mean of these amplitudes is  $\geq 11.1$  mmol/L the subject is considered to have labile diabetes. Where the MAGE fails as a measure of lability is with the subject who has a gradual decline in glucose over the day from 22 to 2 mmol/L. Such a profile will give a MAGE of 20 but such a gradual decline need not be considered truly labile.

Also used in the past has been the M value of Schlichtkrull  but this logarithmic expression of the glucose deviation from a standard glucose level has not been validated. More recently  the advent of continuous glucose monitoring system (CGMS®) has allowed insight into the patterns of glucose. The CGMS® profiles give exquisite details that have been quantified in terms of mean and standard deviation. Determining lability with this process has been more difficult and the suggested method has been the determination of the absolute value of measured glucose minus 5.5 mmol/L. This has the drawback that sustained high glucose levels will result in a high value but the profile may not necessarily be labile. In addition, the technique is currently limited to three days of monitoring and may be less accurate at low glucose levels .

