#### 4.1.2.1 SECONDARY EFFICACY ENDPOINTS

At  $75 \pm 5$  days following the first islet transplant and following each subsequent islet transplant:

- The percent reduction in insulin requirements
- HbA1c
- Mean amplitude of glycemic excursions (MAGE)
- Glycemic lability index (LI)
- Ryan hypoglycemia severity (HYPO) score
- Basal (fasting) and 90-min glucose and c-peptide derived from the mixed-meal tolerance test (MMTT)
- $\beta$ -score
- C-peptide: (glucose X creatinine) ratio
- Acute insulin response to glucose (AIRglu), insulin sensitivity, and disposition index (DI) derived from the insulin-modified frequently-sampled IV glucose tolerance (FSIGT) test
- Glucose variability and hypoglycemia duration derived from the continuous glucose monitoring system® (CGMS)
- Quality of life (QOL) measures

If a third transplant occurs less than 75 days after the second transplant, the 75 day endpoint data for the second transplant will not be collected.

At  $365 \pm 14$  days following the first and final islet transplant:

- The percent reduction in insulin requirements
- HbA1c
- MAGE
- LI
- Clarke score
- HYPO score
- Basal (fasting) and 90-min glucose and c-peptide (MMTT)

- $\beta$ -score
- C-peptide: (glucose X creatinine) ratio
- AIRglu insulin sensitivity, and disposition index (DI) derived from the FSIGT test
- Glucose variability and hypoglycemia duration derived from the continuous glucose monitoring system® (CGMS)
- QOL measures
- The proportion of subjects receiving a second islet transplant
- The proportion of subjects receiving a third islet transplant
- Rate of favorable outcome at each center preparing islets (rate of subjects with an HbA1c < 7.0% and free of severe hypoglycemic events)

Secondary efficacy endpoints measured at  $365 \pm 14$  days following the final islet transplant will include the change in the above measures from the results obtained at  $75 \pm 5$  days following the final islet transplant.

At two years (730+14 days) following the final islet transplant:

- The percent change from baseline insulin requirements
- The number of severe hypoglycemic events from 28 days to two years
- HbA1c
- Clarke score
- Basal (fasting) and 90-min glucose and c-peptide (MMTT)
- $\beta$ -score
- C-peptide: (glucose • creatinine) ratio
- CGMS
- QOL

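### The CGMS glucose variability endpoint is the mean distance from a fixed 5.5 mmol/L, so a fall in mean glucose alone can be reported as reduced variability

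*Protocol*

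**What the plan says.** Section 4.1.2.1 lists "Glucose variability and hypoglycemia duration derived from the continuous glucose monitoring system" as a secondary efficacy endpoint at Day 75 after each transplant and at Day 365 after the first and final transplants. At two years after the final transplant it lists CGMS again, without naming an output.

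Section 9.1.2.9 gives the derivation. Each 72-hour trace is analysed for mean glucose, for "mean glucose variability (absolute value of measured glucose minus 5.5 mmol/L [100 mg/dL"]), for the number and duration of high and low episodes, and for total time in hypoglycemia. No SD, CV or other dispersion about the subject's own mean is listed.

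Section 9.1.1 names "glucose variability (CGMS") as a separate item from glycemic control (HbA1c) and from lability. For lability, section 9.1.2.3 says "Glycemic lability will be assessed by both the MAGE" and the lability index (LI), both from capillary readings.

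Section 1.3.1 discusses the same absolute-difference index and comments: "This has the drawback that sustained high glucose levels will result in a high value but the profile may not necessarily be labile". Just before that, it says CGMS "profiles give exquisite details that have been quantified in terms of mean and standard deviation".

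**The concern.** A measure called variability should respond to how much glucose moves and should not change merely because the whole trace shifts. Distance from a fixed 5.5 mmol/L does not behave that way. The transplant is expected to lower mean glucose, and for any trace staying above 5.5 that alone lowers the index. The result would be reported as reduced variability although the swings had not changed. It would also repeat mean glucose, which the same sentence of section 9.1.2.9 already reports, under a second name.

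Inclusion criterion 8 admits subjects for marked glycemic lability, among other routes. Whether the graft steadies glucose is therefore a question readers will ask of this endpoint.

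**Working it through.** **Inputs.** The index is from section 9.1.2.9, read as the average over sensor readings of |G − 5.5|. The large-swing example is from section 1.3.1. All other traces are constructed for illustration.

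**Reference point.** The protocol equates 10.0 mmol/L with 180 mg/dL, a factor of 18. Then 5.5 × 18 = 99 mg/dL, which agrees with the stated 100 after rounding.

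**What the index contains.** Because |x| = x + 2·max(−x, 0),

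mean|G − 5.5| = (mean G − 5.5) + 2 × mean shortfall below 5.5.

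- If every reading is at or above 5.5, the second term is zero and the index is mean glucose minus 5.5.
- If every reading is at or below 5.5, the index is 5.5 minus mean glucose.
- If the trace crosses 5.5, the second term brings in some information on spread.

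**Applied to traces** (mmol/L):

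| Trace | Mean | SD | Index |
|---|---|---|---|
| Flat 10 | 10 | 0 | 4.50 |
| Smooth wave 10 ± 1 | 10 | 0.7 | 4.50 |
| Smooth wave 10 ± 4 | 10 | 2.8 | 4.50 |
| Alternating 8/12 | 10 | 2.0 | 4.50 |
| Alternating 6/10 | 8 | 2.0 | 2.50 |
| Flat 8 | 8 | 0 | 2.50 |
| Alternating 2/9 | 5.5 | 3.5 | 3.50 |
| 2 for two thirds of the time, 20 for one third | 8 | 8.5 | 7.17 |
| Flat 13 | 13 | 0 | 7.50 |

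1. *No information on spread above 5.5.* The first four traces have SDs from 0 to 2.8 and the same index, 10 − 5.5 = 4.50.
2. *Apparent improvement without change.* Moving from 8/12 to 6/10 changes the index from 4.50 to 2.50, and (4.50 − 2.50)/4.50 = 44%. The SD stays at 2.0.
3. *Misranking.* Moving from 2/9 to flat 10 removes every swing and all hypoglycemia, yet the index rises from 3.50 to 4.50, and 4.50/3.50 − 1 = 29%.
4. *The protocol's own example.* Section 1.3.1 says "swings in glucose values between 2 and 20 and back to 2 mmol/L may give a mean glucose of 8 mmol/L". With two levels, a mean of 8 needs one third of the time at 20. The index is (2/3) × 3.5 + (1/3) × 14.5 = 7.17. Any flat trace above 5.5 + 7.17 = 12.67 mmol/L scores as more variable.
5. *Where the index does respond.* That same swinging trace scores 7.17, against 2.50 for a flat trace with the same mean of 8.

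**Coverage by other measures.** MAGE and LI are endpoints at Day 75 and Day 365 in section 4.1.2.1. Neither is in the two-year list. Appendix 4 schedules only the Clarke score among the calculated indices, while CGMS is still collected. At two years the sensor trace is therefore the only listed source of a variability measure.

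**The case against.** A reader might infer that the index measures glucose level and not variability at all. The documents do not support that. For a trace crossing 5.5 the index carries spread: alternating 2/9 has mean 5.5, so its level term is zero, yet the index is 3.5, equal to the SD. Crossing should be common. Entry requires a severe hypoglycemic event, and the insulin target of 80–120 mg/dL in section 5.3.4 straddles 100 mg/dL. Against this, the study definition of insulin independence allows fasting glucose up to 7.0 and 90-minute glucose up to 10.0 mmol/L, so a successful subject's trace can lie largely above 5.5.

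A reader might also take the 29% as the expected distortion. It is not: three days flat at 10 mmol/L is a constructed extreme, and the figure shows only that misranking is possible.

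Three further points stand in part:

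- MAGE and LI rest on excursions or successive differences, so a flat high profile does not score as labile on them. The mean and hypoglycemia outputs in section 9.1.2.9 would also expose the 2/9-to-flat-10 case. A false conclusion at Day 75 or Day 365 is therefore less likely, but this protection is incomplete at two years.
- Section 1.3.1 presents the index as the suggested method, states its drawback, and does not recommend SD. The choice was informed. It is not an unnoticed error, but section 9.1.2.9 applies the variability label without a remedy.
- SD has its own limits. It ignores time order, so the gradual 22-to-2 decline for which section 1.3.1 faults MAGE would have an SD of about 5.8.

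The last point, and section 4's statement that the companion phase 3 trial has identical endpoint measures, argue against replacing the index. They do not argue against adding SD and CV beside it.

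**Conclusion.** The point holds in a limited form. The quantity labelled glucose variability is the mean distance from 5.5 mmol/L. It contains no information on spread for traces wholly on one side of 5.5, and mixes level with spread for traces that cross it. A fall in mean glucose with unchanged swings can be reported as reduced variability, by 44% in the illustrative 8/12 to 6/10 shift.

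The algebra needs no assumption beyond reading the definition as an average of absolute differences. The size in practice is unknown, because it depends on how much of each real trace lies above 5.5, which the protocol does not give.

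The consequence is modest. This is one of many secondary endpoints in a 10-subject pilot, the primary endpoint and sample size are untouched, and MAGE and LI help at Day 75 and Day 365. The exposure is greatest at two years, where they are not endpoints. It would go too far to say that the trial cannot assess lability or that the endpoint has to be dropped.

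**What to change.** In section 9.1.2.9:

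- Keep mean |glucose − 5.5 mmol/L|, so that the measure stays aligned with the companion phase 3 trial, but relabel it *mean absolute deviation from 5.5 mmol/L*.
- Add the within-subject SD and CV (SD divided by mean) of all readings in the 72-hour trace as the measures of variability, at baseline, Day 75, Day 365 and two years.
- State that any conclusion about glucose variability rests on SD and CV, together with MAGE and LI where these are collected.

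Report SD and CV side by side. When the mean falls and the SD does not change, CV rises: in the 8/12 to 6/10 shift it goes from 2/10 = 20% to 2/8 = 25%.

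Carry the wording into section 4.1.2.1 and the synopsis, and name the CGMS outputs meant at two years.

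The cost is a wording change, a little derivation code on traces already collected, and one or two more secondary summaries without multiplicity adjustment, which section 10.2.2 already accepts for the secondary endpoints. No visit, sample or subject burden is added.
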